7.2.2.2 DISCONTINUATION OF INVESTIGATIONAL MEDICINAL PRODUCT

During the Main Portion, if a subject permanently discontinues study drug at any time prior to completion of Day 57 (see Section 8.4.2), the subject should return to clinic for an End of Main Visit. During the Extension Portion, if a subject permanently discontinues study drug at any time (see Section 8.4.2), the subject should return to clinic for a Final Extension Visit. If a subject discontinues study drug at any time, a 40 day follow up visit is required.

The following procedures will be completed at the End of Main and Final Extension Visits:

- Completion of the following efficacy assessments:
 - 3TUG (in ambulatory subjects only)
 - Proximal MMT
 - Physician Global VAS
 - Patient Global VAS
 - HAQ
 - MDAAT
 - FACIT-Fatigue
- Measurement of weight
- Review and documentation of concomitant medications
- Physical examination
- Vital signs (HR, body temperature, blood pressure in the sitting position)
- 12-lead ECG
- Collection of blood samples for laboratory testing: hematology, chemistry, and coagulation (if applicable)
- Collection of urine sample for urinalysis
- Urine pregnancy testing for females of childbearing potential only
- Record AEs
- Collection of blood samples for the following assessments:
 - ADA sampling
 - PK analysis
 - PD analyses
 - Autoantibody testing
 - Biomarker analysis
- Return of all used and unused study drug syringes to site

All subjects who discontinue study treatment will have a Safety Follow-up Visit 40 days after the last dose of study drug, to collect the following information:

- Review and documentation of concomitant medications
- Physical examination
- Vital signs (HR, body temperature, blood pressure in the sitting position)
- Urine pregnancy testing for females of childbearing potential only
- Record information on ongoing AEs or new SAEs since the last study visit.

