11.4.1.1 ADVERSE EVENTS

Pre-existing conditions that are detected prior to administration of the first dose of study drug will be recorded as part of the medical history. For all subjects, the AE reporting period will start with the first administration of study drug on Day 1 (for SAE reporting period, see Section 11.4.1.2) and will end 40 days following the last dose of study drug (i.e., the End of Main Visit, Day 57 Visit, or Final Extension Visit), after which no new non-serious AEs are to be reported. The subjects will be monitored throughout the study for any AEs, including clinically significant findings at vital signs measurements, spontaneous reports by study subjects, and observations by the study personnel.

When possible, ongoing AEs assessed as related to the study drug will be followed until resolved or stabilized. Subjects visit the clinic 40 days after their last dose to gather information on ongoing AEs and report any new SAEs since the last study visit (see Section 11.4.1.2 for SAE reporting instructions).

All AEs will be recorded in the eCRF. The investigator will assess and record any AE in detail including the date and time of onset, event diagnosis (if known) or sign/symptom, severity, time course (end date or ongoing), relationship of the AE to study drug, and action(s) taken. All AEs should be reported separately (i.e., 1 record per event).

Reporting of AEs is event-based (i.e., an ongoing event will not be closed until resolved or at the end of study). For the AE description, a diagnosis is preferred over symptoms. If no diagnosis can be made, each symptom will be reported as a separate AE.

Abbreviations should be avoided. Descriptive words should be used for ongoing conditions as applicable (e.g., [REDACTED]).

AEs will be coded using Medical Dictionary for Regulatory Activities (MedDRA; Version 20.0 or higher) after the eCRFs have been monitored and signed by the investigator.

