5.6 Safety Analyses

5.6.1 Extent of Exposure

Any analysis related to the exposure will be based the SS.

The number and percentage of participants with cumulative IMP duration (e.g. any duration, ≥ 1 week, ≥ 2 weeks, ≥ 3 weeks,, etc.) will be presented by IMP.

IMP duration = Date of Last Dose – Date of First Dose +1

The duration of exposure to each treatment will be summarized by IMP:

Duration of exposure in years (or Participant Exposure Years (PEY)) = $[(\min(\text{Date of Last Dose} + 40 \text{ days, Last Visit}) - \text{Date of First Dose} + 1)] / 365.25$

Thus, exposure will be adjusted for the 5 half-lives of active treatment which is 40 days.

Duration of exposure (100 participant years) = PEY / 100.

Summaries on the treatment exposure and time at risk in subject years will be given.

Participants which are exposed to both treatments will be presented in either study treatments using the corresponding start and stop treatment date.

The number of doses missed (from the eCRF Study drug administration page after Day 1) will be summarized overall and by IMP.

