5.6.2 Adverse Events

Adverse events will be captured from the time of informed consent signature (only the SAEs) or from the time of first administration (Treatment Emergent Adverse Events) and will be reported if occurred during scheduled or unscheduled visits. As Treatment Emergent AE (TEAE) is defined as an AE starting on or after the time of first administration of study drug or an AE that increases in severity after treatment start, if the event was present at the time of the treatment initiation. Reporting of TEAEs refer to the period until the administration of the last study dose plus 40 days (or last visit depending which occurs first).

AEs will be classified according to the Common Terminology Criteria for Adverse Events (CTCAE) Version 5.0 for severity. For any AE where it is not possible to provide a CTCAE grading, the event will be assessed using a standard intensity classification (mild, moderate and severe). For the purpose of the tabulations all CTCAE severity classifications will be mapped to a mild/moderate/severe grade as described below:

- Grade 1 - Mild
- Grade 2 - Moderate
- Grade 3, 4, 5 - Severe

These will be tabulated together with the AEs that were not classified according to CTCAE criteria i.e., all Grade 1 AEs as per CTCAE criteria will be included in the ‘mild’ category together with those AEs classified as mild as per the ‘standard’ intensity classification.

If a particular AE severity is missing, then this will be listed as missing and treated as missing in summaries. If a participant has experienced more than one TEAE within the same PT, then the AE with the greatest severity will be presented. If a participant reported more than one AE within the same (System Organ Class) SOC then the participant will be counted only once with the greatest severity at the SOC where applicable.

Where dates are missing or partially missing, AEs will be assumed to be treatment-emergent unless evidence exists that does not allow the AE to be treatment-emergent. Handling of missing dates for classification of AEs as TEAEs is described in Section 5.1.1.8.

TEAE summaries will be performed in SS and repeated in SS_{NOCOVID-19} if at least 15% of the participants have at least one AE as ‘Confirmed COVID-19’.

Summaries may also be repeated in SS among participants with at least one TEAT based on the COVID-19 period defined as:

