- Non-Serious TEAEs by PSOC and PT of at least 5% within any IMP (Main Portion) or active treatment (Extension Portion), in SS
- TEAEs by PSOC and PT leading to drug discontinuation, in SS
- TEAEs by PSOC and PT leading to death, in SS

Of note, the following are not considered to be AEs despite requiring hospitalization:

- Pre-existing conditions that, in the opinion of the investigator, did not worsen or progress during study participation
- Routinely scheduled procedures or treatments
- Elective procedures that were scheduled prior to study participation (i.e., signing of the ICF)

Safety tables for the combined Main and Extension Portion of the study, will display the Treatment Emergent Adverse Event Incidence Rate (AEIR) per 100 patient-years of Zilucoplan treatment (thus no placebo arm to be summarized due to limited exposure time as compared to active). Tables will include the PEY per 100 patient years (as defined in Section 5.6.1), number and percentage of participants with a particular TEAE, the exposure adjusted incidence rate (EAIR) followed by 95%CI and the exposure adjusted event rate (EAER):

- EAIR for TEAEs by PSOC and PT, in SS
- EAIR for serious TEAEs by PSOC and PT, in SS

The EAIR is defined as the number of study participants with a specific new TEAE divided by the duration of exposure of all participants (scaled to 100 participant years). The time at risk for a study participant is censored at the date of this event. If a study participant has no events, the total time at risk (i.e. exposure) is used.

Exact Poisson 95% CIs for EAIR are calculated using the relationship between the Poisson and the Chi-square distribution (Ulm, 1990; Fay and Feuer, 1997):

$$\text{Lower Confidence Limit} = x_{2n,\alpha/2}^2/2$$

$$\text{Upper Confidence Limit} = x_{2n(n+1),1-\alpha/2}^2/2$$

where n stands for the number of participants with a specific TEAE for the incidence rate of interest and is the basis for the number of the degrees of freedom for the chi-square quantile for the upper tail probability χ^2 .

The EAER is defined as the total number of TEAEs including repeat occurrences in individual study participants divided by the total time at risk scaled to 100 patient-years. No confidence interval will be computed for the EAER.

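### The protocol contradicts itself on whether new non-serious AEs are collected in the 40 days after last dose, while the SAP counts those days as time at risk

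*Protocol*

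**What the plan says.** **Collection.** Protocol 7.2.2.2 has two visit checklists. At the End of Main and Final Extension Visits, sites record AEs without restriction. At the Safety Follow-up Visit they are told to "Record information on ongoing AEs or new SAEs since the last study visit". The narrower wording recurs in the synopsis, Protocol 7.1, footnotes 1-a, 1-k and 2-i of the Time and Events tables, 11.4.1.2 and 11.4.2.2. It is also in SAP 1.2 and the footnotes to SAP Tables 1-2 and 1-3. The second paragraph of Protocol 11.4.1.1 gives the purpose of the visit as "to gather information on ongoing AEs and report any new SAEs since the last study visit".

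**Reporting period.** The first paragraph of the same section says that AE reporting starts with the first dose and "will end 40 days following the last dose of study drug (i.e., the End of Main Visit, Day 57 Visit, or Final Extension Visit"; the bracket closes there and the sentence continues "after which no new non-serious AEs are to be reported".

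**Analysis.** SAP 5.6.2: "Reporting of TEAEs refer to the period until the administration of the last study dose plus 40 days", or to the last visit if that comes first. SAP 5.6.1 defines exposure as min(last dose + 40 days, last visit) − first dose + 1, and explains: "Thus, exposure will be adjusted for the 5 half-lives of active treatment which is 40 days". This exposure feeds two zilucoplan-only rates in the combined Main and Extension tables: the exposure-adjusted incidence rate (EAIR) and the exposure-adjusted event rate (EAER). SAP 6.3 reports no departures from the protocol.

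**The concern.** The window over which events are counted and the window over which they are collected should be the same. Here the SAP uses one window and the visit instruction describes a narrower one for non-serious events. A site working from the 7.2.2.2 checklist could leave out new non-serious AEs that began after dosing stopped, while the SAP still adds up to 40 days per participant to the denominator. No other scheduled visit falls in that window once dosing has stopped.

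TEAE incidence is the primary safety endpoint, and EAIR/EAER are the planned exposure-adjusted summaries of long-term safety. Sites that read the protocol differently would also collect differently, and the data would not show which reading each site had used.

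**Working it through.** The documents give no AE rate, so there is no planned figure to reproduce. The size follows from the SAP definitions.

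**Inputs**
- Tail added to exposure: up to 40 days (SAP 5.6.1).
- Days on zilucoplan, T, for a participant randomized to zilucoplan: Day 1 to Day 57 gives 57 (Protocol 7.2.2). Day E1 is Day 57, so Day E117 gives 57 + 116 = 173. Main + 18 months (the Extension length in France) gives 57 + 548 = 605.
- c: the share of new non-serious AEs in the tail that are captured. This is an assumption, shown from 0 to 1.
- Event rate: assumed constant, and the same after last dose as before it.

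**EAER** (all events divided by total time at risk): observed/true = (T + 40c)/(T + 40).

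**EAIR**: "The time at risk for a study participant is censored at the date of this event", so only participants without the event contribute the tail. With true rate L per day and c = 0, the mean time at risk on drug is t = (1 − exp(−L·T))/L, and observed/true = t/(t + 40·exp(−L·T)).

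| Dosing ends at | T | Tail share 40/(T + 40) | EAER ratio, c = 0 | EAER ratio, c = 0.5 | EAIR ratio, c = 0, true 100 per 100 PY | EAIR ratio, c = 0, true 20 per 100 PY |
|---|---|---|---|---|---|---|
| Day 57 | 57 | 40/97 = 41.2% | 57/97 = 0.588 | 77/97 = 0.794 | 0.607 | 0.591 |
| Day E117 | 173 | 40/213 = 18.8% | 173/213 = 0.812 | 193/213 = 0.906 | 0.847 | 0.819 |
| Main + 18 months | 605 | 40/645 = 6.2% | 605/645 = 0.938 | 625/645 = 0.969 | 0.975 | 0.947 |

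With c = 1 every ratio is 1.00.

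**Variations**
- A participant who switches from placebo starts zilucoplan at Day E1, so T is shorter: 40/(117 + 40) = 25.5% at Day E117 and 40/(548 + 40) = 6.8% at 18 months.
- Dosing that ends before Day 57 gives a larger share than 41%.
- If the rate after last dose is half the on-drug rate, the Day 57 loss relative to full capture is 1 − 57/(57 + 20) = 26%. A higher rate after last dose would make the loss larger.
- An End of Main or Final Extension Visit held some days after last dose still records all AEs, which shortens the uncollected stretch below 40 days.

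These are per-participant figures. The tabulated rates pool events and time over participants, so long exposures dominate. Because exposure is capped at the last visit, participants still on drug at a cut-off add no full 40-day tail.

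**The case against.** The strongest reply is that non-serious AEs are reportable throughout the 40 days. The clause "after which no new non-serious AEs are to be reported" makes little sense unless they are reportable until then, and the bracket can be read as naming the visits at which the last dose falls. The amendment summary says the sentence was updated so that AE reporting ends 40 days after last dose, to comply with sponsor safety guidance. Section 11.4.1.1 also requires all AEs to go into the eCRF.

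There is also a practical route. The Safety Follow-up Visit includes a physical examination and vital signs. Protocol 10.2.1 has clinically significant findings after Day 1, and injection site reactions, recorded as AEs whatever their seriousness. SAP 5.6.4.4.1 carries examination findings to last dose + 40 days or last visit.

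This reply stands to the extent that under-capture is not certain. A reader might infer that new non-serious AEs cannot be recorded after last dose, or that the rates are necessarily understated. The documents support neither. A reader might also infer that the primary safety comparison has a diluted denominator. It does not: SAP 5.6.2 presents Main Portion TEAEs as participants, percentages and event counts, without person-time. The same collection rules apply to both arms, and only participants who do not enter the Extension have a Main Portion follow-up period (SAP 5.1.1.2.2).

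The reply does not remove the conflict. One sentence with an ambiguous bracket stands against an instruction repeated across the protocol and SAP, and 7.2.2.2 itself contrasts unrestricted AE recording at one visit with restricted recording at the next. An examination on one day can also miss an event that began and resolved earlier in the window.

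**Conclusion.** The contradiction is in the text and should be resolved. Its effect on the results is a risk that depends on site practice, not a demonstrated bias.

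The 41%, 19% and 6% figures for EAER are the zero-capture ends of ranges that run down to no loss at full capture, and they assume a constant event rate. With half the events captured, the shortfalls are 21%, 9% and 3%. EAIR is affected less: at a true rate of 100 per 100 patient-years, Main + 18 months would read 97.5 even with no capture.

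The exposure-adjusted part of the concern is confined to the zilucoplan rates in the combined Main and Extension tables, including the EAIR table for TEAEs of interest in SAP 5.6.3. Serious TEAE rates are unaffected, because new SAEs are collected to 40 days on either reading. In the Main Portion tables, the most that could happen is some missed non-serious events among participants who do not continue into the Extension.

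**What to change.** **Preferred.** Have the Safety Follow-up Visit record all new AEs, serious and non-serious, since the last visit. Change Protocol 7.2.2.2 and footnotes 1-a, 1-k and 2-i. Bring the synopsis, 7.1, 11.4.1.1 (second paragraph), 11.4.1.2, 11.4.2.2, SAP 1.2 and SAP Tables 1-2 and 1-3 into line. Clarify or delete the bracket in 11.4.1.1. The visit already takes place, so the cost is protocol, SAP and eCRF-instruction wording plus a note to sites.

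**If collection cannot change.** Add a sensitivity version of the all-TEAE EAIR/EAER tables in which event counting and time at risk both end at the last visit where all AEs are recorded. Keep + 40 days for the serious TEAE tables. Both sides must move together: ending time at last dose while still counting TEAEs to + 40 days would create the opposite mismatch. Splitting the window by seriousness within a table would not work either, because the SAP plans no separate non-serious EAIR table and one preferred term can hold both kinds of event. The cost is one extra derivation and a small set of repeat tables.

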7.3 EARLY STUDY TERMINATION

The end of study, or study termination, is defined as the time at which the last subject has performed their last visit (LSLV). Following LSLV, all remaining data will be collected

in the appropriate case report forms (see Section 14.3) and the study results will be summarized in the clinical study report (CSR) (see Section 14.5).

The Sponsor may terminate this study early (in its entirety, in part, or at one or more study sites) for reasonable cause provided that written notice is submitted in advance of the intended termination. The investigator may also terminate the study at the site for reasonable cause, after providing written notice to the Sponsor in advance of the intended termination. Advance notice is not required by either party if the study is stopped due to safety concerns. If the Sponsor terminates the study for safety reasons, the Sponsor will immediately notify the investigator and subsequently provide written instructions for study termination.

If the Sponsor terminates or suspends the study, all applicable Competent Regulatory Authorities will be informed as per applicable legislation.

7.4 STUDY CONDUCT DURING COVID-19

The protocol-mandated visit schedule should be followed to the extent possible, based on the judgment of the investigator. However, during the COVID-19 outbreak or under other exceptional circumstances, remote follow-up will be conducted and the subjects will be contacted by telephone/video contact to assess as many details as possible, according to the protocol scheduling, to verify that the subject is suitable for continuing study treatment. Some procedures may be collected by other remote means if feasible and/or acceptable per local guidelines. Study sites should make efforts to inform the sponsor or the CRO in the event that protocol procedures cannot be completed due to COVID-19.

In those situations when the subject cannot return to the study site, the investigators will assess the subject's safety by telephone/video contact. Based on information gathered from the telephone/video contact, investigators will confirm whether the subject could continue the current IMP treatment after the assessment. If the subject is suitable for study treatment continuation, the investigator or designee will assess if the subject agrees to provide name, address, telephone number, and email to the appointed courier. The subject will confirm his/her consent by email or verbally in order to receive IMP via courier. If the email option is not possible, the site must obtain consent via phone and document it in the medical record.

If the shipment is agreed, the investigator or designee will clearly explain to the subject everything needed regarding the handling (in case of inconsistencies at delivery) and administration of the study drug and how to return all unused IMP to the study site at the next on-site visit. Only after approval by the study staff for the correct shipment will the subject start taking the treatment. The whole process and communication with subject will be documented in the subject's medical source record. Changes in the study treatment supply in this situation are described in Section 9.2.1.1.

Ad hoc subject contact may be warranted to understand the current health status of the subjects, to follow up on AEs, and inform them of any protective measures taken by the clinical site as a result of the COVID-19 pandemic (e.g., any measures that may limit access to the site or may require additional actions by the subject prior to entry to the site).

If a subject needs to be discontinued and cannot come into the clinic, a visit will be scheduled to perform final safety assessments as soon as possible.

If a subject visits another facility for a medical issue, the investigator should request contact with the physician providing care to provide a detailed explanation of the subject's condition and his/her participation in the clinical study. Subjects or caregivers shall be reminded to completely collect and keep records of this visit.

Deviations to data collection including inability to perform some assessments, or alternative methods of assessment, such as phone calls, should be recorded in the source documentation and notated as "not done" in the eCRF.

8 SELECTION OF STUDY POPULATION

8.1 INCLUSION CRITERIA

To be eligible for this study, subjects must meet **ALL** of the following inclusion criteria:

1. Male or female \geq 18 years and $<$ 75 years.
2. Able to provide informed consent, including signing and dating the informed consent form (ICF).
3. Clinical diagnosis of IMNM (Immune-Mediated Necrotizing Myopathy).
4. Positive serology for anti-HMGCR or anti-SRP autoantibodies.
5. Clinical evidence of weakness (\leq grade 4 out of 5) on manual muscle testing in at least one proximal limb muscle group.
6. CK (creatinine kinase) of >1000 U/L at Screening.
7. No change in corticosteroid dose for at least 30 days prior to Baseline or anticipated to occur during the first 8-weeks on study.
8. No changes in immunosuppressive therapy, including dose, for at least 30 days prior to Baseline or anticipated to occur during the first 8-weeks on study.
9. Female subjects of childbearing potential must have a negative serum pregnancy test at Screening and a negative urine pregnancy test within 24 hours prior to the first dose of study drug.
10. Sexually active female subjects of childbearing potential (i.e., women who are not postmenopausal or who have not had a hysterectomy, bilateral oophorectomy, or bilateral tubal ligation) and all male subjects (who have not been surgically sterilized by vasectomy) must agree to use effective contraception during the study. Postmenopausal women are, for the purposes of this protocol, defined as women who have gone 12 consecutive months without menstruation.

